3.3.3.3. Quality of life questionnaires: PROMs and PREMs

Through the dedicated ATS application, the answers to the EQ-5D-5L and EORCT QLQ-LC29 questionnaires and to the PREMs questionnaire (**Annex 3**) will be collected in an electronic database. This database will have a unique ID code for the 4 questionnaires relating to each patient (generated at first administration and entered by the patient in the two subsequent self-administrations of the other three questionnaires). The database will be subject to record linkage with the administrative databases for data collection of the variables in Table 4. Furthermore, the variables in Table 5 will be collected by the referring clinicians. The collection methods will be the same used in the retrospective study.

3.3.4. Data analysis

3.3.4.1. Power of the study

To study the efficacy, data from the retrospective and prospective study will be analyzed jointly. For the retrospective part, approximately 5,000 patients operated on for lung cancer in the participating centers from 01/01/2016 to 12/31/2021 will be included. Based on the average of approximately 450 subjects operated on in the participating centers over 6 months during the years 2019-2021, a sample of 400 subjects eligible for enrollment in 6 months during 2022 was considered in the prospective observational study. As regards the statistical power in the analysis of the primary efficacy outcome, i.e. long-term survival, the calculation was based on an assumption of non-inferiority. The following formula was used to calculate potency in survival studies which is based on the hazard ratio [37].

$$1-\beta=\Phi(z-z_{1-\alpha}), z=(\ln(\theta)-\ln(\theta_0))\sqrt{np_Ap_Bp_E}$$

Where:

- θ_0 = hazard ratio under the null hypothesis, set equal to 1
- θ = observed hazard ratio
- pE = probability of event, i.e. death, set equal to 0.8 on the basis of epidemiological data from the ATS cancer registry
- pA = proportion of treated by robotic surgery equal to 0.12 on the basis of the data present in the SDOs for the year 2019 and of the preliminary information provided by the participating centers

pB = 1-pA

- n = sample size, equal to 5400
- Φ = distribution function of the standard normal
- A = I-type error, set equal to 0
- $1-\beta =$ statistical power

By varying the observed HR of VATS death versus the observed control group between 1.08 and 1.15, the statistical power ranged from 0.5 to 0.91. The power calculation was performed using R (v4.1.2, R Core Team 2021, Vienna, Austria.)

As regards the analysis of quality of life, the prospective study will take into consideration patients undergoing three types of surgery: robot-assisted, VATS, and open surgery. Specifically, the number of groups enrolled is assumed starting from the average of interventions carried out in the period 2016-2021. Therefore, for the prospective study, we estimated 48 subjects operated with robotic surgery, 94 with VATS, and 258 with open surgery. Literature relating to the comparison of the quality of life in patients operated with VATS and open surgery [38] illustrates the analysis of the EQ-5D questionnaire at different post-intervention time points. The data of our interest relate to the mean and standard deviation of the Visual Analogue Score of the EQ-5D questionnaire administered 4 weeks after the intervention; respectively: VATS 78.1, Open 73.5. The one-way analysis of variance methodology was used to study the power. For robotic surgery, since the necessary data in the literature are not available, we assumed an average of the Visual Analogue Score EQ-5D ranging from 80 to 83, which allowed the calculation of the estimated power illustrated in the table below. A standard deviation of 17.2 was assumed for all three groups based on literature data [38]. For the analysis of statistical power, we used the PROC POWER procedure, statement ONEWAYANOVA of the SAS software (v. 9.4, SAS Institute Inc., Cary, NC, USA).

Mean Visual Analogue Score EQ-5D	Power
80	0.669
81	0.790
82	0.880
83	0.939

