3.3.4.2. Efficacy study

Since this is an observational study, all analyses must take confounding into account. For each outcome, a Direct Acyclic Graph (DAG) will be prepared, discussed by surgeons and epidemiologists, i.e. a graph that allows hypothesizing the causal relationship between intervention and outcome taking into account potential confounding factors, measurable or not. On the basis of this graph, which underlies a causal model, the variables to be included in the multinomial regression model will be selected for estimating the probability of being treated with each surgical modality as a function of potential confounders (known as propensity score). Among the variables that will be considered to define the DAGs are age, gender, performance status, treatment center and tumor characteristics. The inverse of this estimated probability will be used as weight in the regression models (inverse probability weighted, IPW) which will have the outcome as the dependent variable and the treatment modality as the independent variable: robotics, VATS and thoracotomy (reference). Differences in the duration of surgery and hospitalization will be analysed using an IPW generalized linear regression model. The 30-day odds ratio (OR) of death for VATS and robotic surgery versus thoracotomy will be estimated by means of an IPW logistic regression model. Relative survival will be evaluated using a Cox IPW model and expressed both in terms of hazard ratio (HR) and as one and 5 year survival. For inpatient reoperation, the need for conversion to thoracotomy for VATS vs. robotic surgery and major complications by type of surgery, which are expected to be rare events, a we will consider a IPW zero-inflated (Poisson or negative binomial) approach. All estimates will be presented together with 95% confidence intervals obtained from a robust standard error [39]. The same analyses, if allowed by the study number, will be repeated in the three surgical subgroups (atypical and segmental resection, lobectomy, pneumonectomy), in subjects aged less than or equal to 65 years vs. superior, in patients with performance status of 0 vs. 1 vs. 2. Sensitivity analyses will be carried out using alternative models for the probability of estimating the type of intervention.

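### The survival power in 3.3.4.1 is called non-inferiority but has a null hazard ratio of 1 and no margin, and its result is labelled VATS although it was computed with the robotic share (minor)

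*Combined protocol and SAP*

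**What the plan says.** Section 3.3.4.1 states that, for long-term survival, "the calculation was based on an assumption of non-inferiority". The inputs listed under its formula include the "hazard ratio under the null hypothesis, set equal to 1", an HR described as observed, an event probability of 0.8, n = 5,400 and "pA = proportion of treated by robotic surgery equal to 0.12", with pB = 1 − pA. The range examined is introduced with "By varying the observed HR of VATS death versus the observed control group between 1.08 and 1.15". For that range the section reports that "the statistical power ranged from 0.5 to 0.91".

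The quality-of-life part of the same section gives expected numbers by approach: "we estimated 48 subjects operated with robotic surgery, 94 with VATS, and 258 with open surgery".

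Section 3.3.4.2 estimates survival in a weighted Cox model whose treatment factor is "robotics, VATS and thoracotomy (reference"), with 95% confidence intervals. It gives no margin and no rule for concluding non-inferiority. Sections 2.1 and 3.4.1 also call for robotic surgery to be compared with VATS.

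**The concern.** A non-inferiority calculation needs a margin above 1 as the null value and an assumed true HR. This one has a null of 1 and an alternative above 1, which is the set-up for detecting harm. The sentence giving the result also names a treatment, VATS, that does not match the share used in the formula, and pB pools VATS with open surgery although the Cox model takes thoracotomy alone as reference.

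Two things are at stake. A reader who takes the sentence at its word attaches 0.50 to 0.91 to the wrong hypothesis and the wrong comparison. And if a non-inferiority statement on survival were ever made, no criterion would have been fixed in advance.

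**Working it through.** **Inputs.** n = 5,400, pA = 0.12, pE = 0.8 and θ0 = 1, all from 3.3.4.1. The printed type I error is not legible as a usable value and is not counted as an error; it is inferred below. The formula uses z(1−α), so it is one-sided.

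**1. Reproduce the plan's figure.** Power = Φ((ln θ − ln θ0) × S − z), with S = √(n pA pB pE) = √(5,400 × 0.12 × 0.88 × 0.8) = √456.2 = 21.36.
- θ = 1.08: 0.07696 × 21.36 = 1.644; Φ(1.644 − 1.645) = 0.4996.
- θ = 1.15: 0.13976 × 21.36 = 2.985; Φ(2.985 − 1.645) = 0.910.

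This matches the stated range at one-sided 5%. At one-sided 2.5% the result would be 0.38 and 0.85, which does not match.

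**2. Test the VATS label.** The VATS share is 94/400 = 0.235, and the robotic share 48/400 = 0.12. With pA = 0.235, S = 27.87 and power is 0.69 to 0.99. The published range therefore belongs to robotic surgery.

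**3. Test the non-inferiority label.** With θ0 = 1, the printed formula returns 0.05 at θ = 1 and 0.0005 at θ = 1/1.08. Its power falls as survival in the index group improves, whereas non-inferiority power should rise. Entering a margin of 1.15 as θ0 with θ = 1 does not help: the printed sign then gives 1.8 × 10⁻⁶. The non-inferiority form is Φ((ln M − ln true HR) × S − z). With M from 1.08 to 1.15 and a true HR of 1, it gives the same 0.50 to 0.91. The unstated true HR matters: at M = 1.15, with n = 5,400 and pA = 0.12, power is 0.99, 0.91 or 0.62 for a true HR of 0.95, 1 or 1.05 (illustrative values).

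**4. Change the comparator.** Assumption: the 48/94/258 split applies to all 5,400, giving 648 robotic, 1,269 VATS and 3,483 open. Robotic versus thoracotomy then has n = 4,131, pA = 648/4,131 = 0.157 and S = 20.91. At one-sided 5%, power is 0.486 and 0.899, about 0.01 below the stated figures.

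**5. Match the level to the planned 95% intervals** (two-sided 5%, z = 1.960, pE = 0.8, same assumed split):

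| Comparison | n | pA | S | HR 1.08 | HR 1.15 |
|---|---|---|---|---|---|
| Robotic vs thoracotomy | 4,131 | 0.157 | 20.91 | 0.36 | 0.83 |
| Robotic vs VATS | 1,917 | 0.338 | 18.52 | 0.30 | 0.74 |

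**6. Vary the event probability** (robotic vs thoracotomy, two-sided 5%; both values assumed). At pE = 0.6, S = 18.11 and power is 0.29 to 0.72. At pE = 0.4, S = 14.78 and power is 0.21 to 0.54.

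**The case against.** The strongest defence is that this is a labelling slip. Section 3.3.4.1 defines pA as the robotic share, so VATS in one sentence is most simply a mistaken word. If 1.08 to 1.15 were meant as margins with a true HR of 1, the numbers are right and only the roles of θ and θ0 are misdescribed. Replacing all other patients by thoracotomy moves power by about 0.01. Section 3.1 takes every eligible patient, so power does not set the cohort size. The Cox estimates and the cost-effectiveness ratios use neither the power nor a margin.

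Most of this stands, and it is why the point is minor. It does not remove the defect: the text calls 1.08 to 1.15 observed HRs and 1 the null, and a reader should not have to work backwards from the result to learn the hypothesis and the comparison.

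The defence is also right about replacement figures. The 48/94/258 split is for the prospective part, and the plan describes its basis as "the number of groups enrolled is assumed starting from the average of interventions carried out in the period 2016-2021", whereas pA = 0.12 is sourced from 2019 discharge data and information from the centres. The retrospective 5,000 are described as lung cancer patients, while the prospective part enrols anyone having the listed lung operations. Figures built on that split can only illustrate.

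**Conclusion.** The survival power statement is wrong as written for the hypothesis and comparison it names; the correction is minor. The range 0.50 to 0.91 is power to detect an excess hazard of 1.08 to 1.15 for robotic surgery against all other patients, at a one-sided 5% level inferred from the reproduction. It is non-inferiority power only under a reading that the plan does not state.

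Three stronger readings are tempting, and the documents do not support them.
- A reader might infer that the power was computed for VATS and is numerically wrong. The defined pA and the reproduction show that it was computed for robotic surgery, and the arithmetic is sound.
- A reader might infer that the survival analysis is compromised. Neither the cohort nor the Cox model depends on this calculation.
- A reader might infer that a non-inferiority conclusion will be drawn without a criterion. No section announces one; 3.3.4.2 plans HRs with confidence intervals.

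The illustrative 0.36 to 0.83 and 0.30 to 0.74 rest on the assumed split and pE = 0.8. They are upper values: they ignore variance inflation from the inverse probability weights, and they fall if fewer than 80% of patients die by the end of follow-up. The latter is possible, since these are operated patients, metastatic cases are excluded from the malignant-tumour cost-effectiveness evaluation (3.1), and Table 4 takes vital status at the end of 2022.

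**What to change.** In 3.3.4.1:

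1. Replace the VATS label with robotic surgery and name thoracotomy as comparator, as in 3.3.4.2. Report robotic versus VATS as well, since 2.1 and 3.4.1 compare them.
2. Preferably delete the non-inferiority wording and restate the figure as power to detect a difference at two-sided 5%, in line with the planned 95% intervals. If a non-inferiority conclusion is intended, state a justified margin M and an assumed true HR, and use Φ((ln M − ln true HR) × √(n pA pB pE) − z(1−α)). Add to 3.3.4.2 that non-inferiority is concluded only if the upper confidence limit of the HR lies below M, with the interval matched to α.
3. Recompute with the sponsor's actual counts by approach, state α and its sidedness, and show how the result varies with pE.

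The cost is some rewording and one recalculation, with no new patients, data or analyses. The downside is a lower stated power and, only if non-inferiority is kept, the need to agree a margin.

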In Europe, lung cancer remains in second place among the most frequent neoplasms in men with 14.2% in 2020, after prostate cancer, while it is in third place with 9.1% in women, after breast cancer and colorectal cancer. Italy reflects the European trend, with 14.1% in men and 7.3% in women [10]. However, in some countries, such as the United Kingdom and Northern Europe, it is now in second place also in women [11]. As regards mortality, lung cancer causes 20.4% of deaths from cancer, remaining the most frequent cause of death from cancer. In fact, five-year survival for lung cancer is still around 18%, respectively 15% for men and 21% for women; this is also due to the high percentage of advanced stage diagnoses [12]. NSCLC represents 80-90% of cases of lung cancer, while SCLC frequency is around 14% [13,14]. As far as Italy is concerned, in 2020 lung cancer was the first cause of cancer mortality in men (23.9%) and the second in women (12.5%) [10]. In the ATS of Milan area in the three-year period 2016-2018, only 23.4% of lung cancers for all ages were diagnosed in stage I and II, and 76.6% in stage III and IV [15]. When the tumor is resectable, and the patient can undergo surgery, the most indicated treatment for this kind of tumor is surgical removal. The National Institute for Clinical Excellence (NICE) recommends to offer surgical treatment to all patients with NSCLC up to stage IIIB. Furthermore, the NICE guidelines suggest lobectomy as a curative intervention when possible, not specifying a preference between the open and the thoracoscopic approach (NICE Guideline 2019). On the contrary, the European Society of Medical Oncology (ESMO) specifies that VATS is the preferable approach in stage I tumors. However, this recommendation has a level of evidence V (studies without control groups, case reports, and expert opinions) and a rating C (insufficient evidence of efficacy).

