3.3.3. Collected variables

3.3.3.1. From administrative databases

The staff of the Epidemiology Unit involved in the study will extract the information specified in Table 4 from the current administrative databases of the ATS of Milan. Subsequently, it will perform the deterministic record linkage on a unique key (fiscal code) and will anonymize the dataset for the analysis, removing the tax code, deleting the dates once the time intervals necessary for the analysis have been calculated (age, length of hospitalization, length of post-operative stay, etc.), and assigning a random ID to the patient. Separate copy of correspondence between social security number and random id will be kept in a separate password protected file.

Data flow	Data relating to	Variables
Hospital Discharge	Patient	Civil status, study level
Summary (SDO)	Hospital admission	Admission date, intervention date, discharge date, type of discharge, within hospital transfers
	Diagnoses and complications	All ICD-9-CM diagnosis codes present in a SDO
	Procedures	DRGs, ICD-9-CM procedure codes, procedure date
Patient registry	Patient	Sex, birth date, city of residence, vital status at 2022/12/31
SDO, outpatient services, pharmaceuticals, exemptions	Patient comorbidities	Charlson comorbidity index calculated through the algorithm in use at the Epidemiology Unit
Cancer registry	Cancer	Histology (morphological code ICDO3, margins of resection, number of mediastinal lymph nodes removed, number of positive mediastinal lymph nodes, stage at diagnosis)

Table 4 Variables collected from administrative databases

3.3.3.2. From the data provided by the centers through a dedicated platform made available by the ATS of Milan

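### The survival power calculation assumes 80% of all 5,400 patients will have died, which follow-up to 31/12/2022 cannot be expected to deliver, so the stated power is too high

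*Combined protocol and SAP*

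**What the plan says.** Section 3.3.4.1 treats long-term survival as the primary efficacy outcome and analyses the retrospective and prospective patients together. The inputs are "n = sample size, equal to 5400" (about 5,000 operated in 2016-2021 plus 400 in 2022), "pA = proportion of treated by robotic surgery equal to 0.12", and "pE = probability of event, i.e. death, set equal to 0.8 on the basis of epidemiological data from the ATS cancer registry". For hazard ratios from 1.08 to 1.15 the section reports power from 0.5 to 0.91. The type I error reads "A = I-type error, set equal to 0" in the text available to us, which may be a loss in extraction.

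Two other places bear on the event probability. Table 4 (section 3.3.3.1) takes "vital status at 2022/12/31" from the patient registry. The epidemiology part of section 1 states that "five-year survival for lung cancer is still around 18" percent, and adds that "this is also due to the high percentage of advanced stage diagnoses". That is the only overall survival figure in the document, and it is not specific to operated patients.

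**The concern.** In this formula n × pE is the expected number of deaths, so pE has to be the share of the analysed patients who are dead by the vital-status cut-off. The plan names a source for 0.8 but not the population or time horizon it describes. The value is close to 1 − 0.18 = 0.82, the five-year mortality of all lung cancer.

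The analysed patients differ from that population in two ways. All were operated on, and section 3.1 excludes metastases at diagnosis from the cost-effectiveness evaluation in malignant tumours, whereas 76.6% of lung cancers in the ATS area were stage III-IV (section 1). Many also have well under five years of follow-up.

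The precision of the hazard ratio depends on the number of deaths. If these are overcounted, readers are told that the study can detect a smaller survival difference than it can, and a null result is more easily over-read.

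**Working it through.** **1. Reproduce the stated power.** The plan's formula with a null hazard ratio of 1 is power = Φ(ln(HR) × √(n × pA × pB × pE) − z).

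- n × pA × pB = 5,400 × 0.12 × 0.88 = 570.24. With pE = 0.8 the root is √456.19 = 21.36.
- HR 1.08: 0.0770 × 21.36 = 1.644. HR 1.15: 0.1398 × 21.36 = 2.985.
- With z = 1.645 (one-sided alpha 0.05) power is 0.4996 and 0.910, as stated. With z = 1.96 it is 0.376 and 0.847, which does not match.

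The arithmetic is therefore right, and the alpha used was evidently one-sided 0.05. Deaths implied: 0.8 × 5,400 = 4,320.

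**2. Event probability under the plan's calendar.** Let F(t) be the probability of death by t years. With even accrual,

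pE = [5,000 × mean of F over 1-7 years + 400 × mean of F over 0-1 year] / 5,400.

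F is taken as Weibull, fixed so that five-year survival is 18%. The shape is an assumption: 1 is a constant hazard, and values below 1 put more deaths early.

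Constant hazard: λ = −ln(0.18)/5 = 0.343.

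- Mean over 1-7 years: 1 − (e^(−λ) − e^(−7λ))/(6λ) = 1 − (0.710 − 0.091)/2.058 = 0.699.
- Mean over 0-1 year: 1 − (1 − 0.710)/0.343 = 0.153.
- pE = (5,000 × 0.699 + 400 × 0.153)/5,400 = 0.659, or 3,557 deaths.

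The second accrual pattern below takes at face value the "average of approximately 450 subjects operated on in the participating centers over 6 months during the years 2019-2021": 6 × 450 = 2,700 operated in 2019-2021, leaving 2,300 in 2016-2018.

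| Accrual | Shape | pE | Deaths | Power, HR 1.08 | Power, HR 1.15 |
|---|---|---|---|---|---|
| As stated in plan | – | 0.80 | 4,320 | 0.50 | 0.91 |
| Even | 1 | 0.659 | 3,557 | 0.439 | 0.856 |
| Even | 0.6 | 0.717 | 3,870 | 0.465 | 0.881 |
| Even | 0.5 | 0.733 | 3,959 | 0.472 | 0.887 |
| 2,300 + 2,700 | 1 | 0.648 | 3,500 | 0.434 | 0.851 |
| 2,300 + 2,700 | 0.5 | 0.728 | 3,930 | 0.469 | 0.885 |

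**3. What would make 0.8 true?** For shapes 1 to 0.5, five-year survival in this cohort would have to be 5.5% to 11.9% with even accrual, or 4.9% to 11.5% with the other pattern. Both are worse than the all-stage 18%.

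**4. If operated patients live longer.** The document gives no survival figure for them, so these values are illustrative assumptions (constant hazard, even accrual). The last column is the hazard ratio at which power equals the stated 0.91, exp(2.985/√(570.24 × pE)). With the plan's pE it is 1.15.

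| Assumed five-year survival | pE | Power, HR 1.08 | Power, HR 1.15 | HR for power 0.91 |
|---|---|---|---|---|
| 30% | 0.549 | 0.389 | 0.796 | 1.18 |
| 40% | 0.465 | 0.348 | 0.736 | 1.20 |
| 50% | 0.384 | 0.306 | 0.664 | 1.22 |
| 60% | 0.305 | 0.264 | 0.578 | 1.25 |
| 70% | 0.227 | 0.221 | 0.478 | 1.30 |

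**The case against.** The documented loss is small. At 18% survival, power falls by roughly 2 to 7 points within a range that already runs from 0.5 to 0.91. The large losses rest on survival values that are not in the document. This stands, and the two sets of figures should be kept apart.

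The 0.65-0.73 range depends on the curve. With 18% survival and even accrual, shape 1.3 gives 0.62 and shape 0.3 gives 0.77 (power 0.486 and 0.900). This also stands, but no plausible shape rescues 0.8. Getting there requires one-year survival of about 0.23, which is not credible in patients selected for resection.

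The 18% follows European figures in section 1, whereas 0.8 is attributed to the local registry, which we cannot see. The document therefore shows that 0.8 is unexplained and does not fit the calendar; it does not show the true value. The 450 per six months may also include surgery other than for lung cancer, but that accrual pattern moves pE by only about 0.01.

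The power statement has other faults: it is called non-inferiority but has no margin, and it labels the hazard ratio as VATS while pA is the robotic share. These are separate, and correcting them would not justify 0.8.

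**Conclusion.** The concern holds. An event probability of 0.8 for all 5,400 patients is unsupported and, given vital status at 31/12/2022, too high. Under the document's own 18% survival and Weibull shapes 0.5 to 1, expected deaths are about 3,500-3,960 rather than 4,320. Power is 0.43-0.47 at HR 1.08 and 0.85-0.89 at HR 1.15.

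The direction is firm. The size depends on the curve shape and, above all, on survival after resection, which the document does not give; survival above 18% makes the overstatement larger. The consequence is limited to the power statement: the calculation does not set the sample size, and section 3.3.4.2 reports 95% confidence intervals. It should be corrected, but it does not threaten the study.

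**What to change.** In section 3.3.4.1, replace n × pE by expected deaths D = 5,000 × p1 + 400 × p2. Here p1 is the proportion dead by the vital-status cut-off among patients operated in 2016-2021, and p2 is the corresponding proportion for 2022 operations with under one year of follow-up. Take both from the registries the promoter already holds, in the same population that n counts, and report the stage mix and follow-up behind them. State the alpha actually used, and give the power range and detectable hazard ratio over a plausible range of D.

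The cost is one registry query and a change of wording, and the stated power becomes less favourable. Enrolment, analysis and patient burden stay as they are. Moving the vital-status date to gain deaths would be a separate decision, since it would delay the final analysis.

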2. OBJECTIVE

2.1. PRIMARY OBJECTIVE

The objective of the analysis is to compare the cost-effectiveness profile of robotic surgery with that of thoracotomy and VATS in the surgical treatment of operable lung cancers in the adult population of the ATS of Milan.

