3.4.1. Economic evaluation outcomes

The results of the cost estimates for each surgical approach will be summarized in tables and presented graphically. The outcome of the cost-effectiveness (CEA) and cost-utility (CUA) analysis will be the incremental cost-effectiveness ratio (ICER); in terms of cost per year of life gained for the first case and in terms of cost per QALYs earned for the second. The ICER of robotic surgery and VATS versus open surgery and the ICER of robotic surgery versus VATS will be calculated. A cost-effectiveness plan will also be constructed for these comparisons. Since the ICER alone cannot answer the question of whether a technology is cost-effective per se, it will be compared with a value in euros that society is willing to pay for an additional QALY earned ("societal willingness-to -pay"). Since there are no Italian regulatory references for willingness-to-pay, the references of NICE (£20-30,000), those of the Italian Association of Health Economics (€25-40,000) and the ICER calculated for dialysis (€50,000) will be used. Lastly, if the technology is cost-effective in at least one subgroup, a budget impact analysis will be carried out.

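### The survival power of 0.50–0.91 is for robotic surgery against all other approaches pooled, a comparison the plan never makes; robotic versus VATS has about 0.41–0.83 on the same inputs

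*Combined protocol and SAP*

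**What the plan says.** The primary objective (section 2.1) is to "compare the cost-effectiveness profile of robotic surgery with that of thoracotomy and VATS in the surgical treatment of operable lung cancers", which names two comparators. Section 3.3.4.2 keeps them apart in the weighted outcome models, with "the treatment modality as the independent variable: robotics, VATS and thoracotomy (reference" category). Section 3.4.1 does the same for the incremental cost-effectiveness ratios: "The ICER of robotic surgery and VATS versus open surgery and the ICER of robotic surgery versus VATS will be calculated".

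The survival power calculation in section 3.3.4.1 has only two groups. It takes "pA = proportion of treated by robotic surgery equal to 0.12", defines pB as the complement of pA, and uses "n = sample size, equal to 5400". The event probability is "set equal to 0.8 on the basis of epidemiological data from the ATS cancer registry", and the null is a "hazard ratio under the null hypothesis, set equal to 1". The result is a single power range, 0.5 to 0.91, for hazard ratios from 1.08 to 1.15. The sentence reporting it describes the varied hazard ratio as that of VATS against a control group.

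The quality-of-life part of the same section gives the expected numbers by approach for the 400 prospective patients: "we estimated 48 subjects operated with robotic surgery, 94 with VATS, and 258 with open surgery". It bases them on the average of operations in 2016–2021.

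**The concern.** Because pB is the complement of the robotic share, the control group in the power formula is every non-robotic patient, 0.88 × 5400 = 4752, with VATS and open surgery merged. That is not a comparison the study will estimate. Each planned robotic contrast uses only part of the 5400. Robotic versus VATS leaves out the open group, which is 258/400 = 64.5% of patients on the plan's split.

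Survival supplies the life-years in each cost-effectiveness ratio, and robotic versus VATS has a ratio of its own. A reader of section 3.3.4.1 would take 0.50–0.91 as the power for the study's question, although no figure is given for either pairwise comparison.

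**Working it through.** **Inputs.** From section 3.3.4.1: n = 5400, pA = 0.12, pB = 0.88, pE = 0.8, null hazard ratio 1, hazard ratios 1.08 to 1.15. The split 48/94/258 of 400 is in the same section, under quality of life. The type I error reads 0 in the available text, possibly a truncated figure, so it has to be inferred.

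**Formula (the plan's own, with null hazard ratio 1).** Power = Φ(ln(HR) × √(n·pA·pB·pE) − z₁₋α).

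**Step 1: reproduce the stated range.** n·pA·pB·pE = 5400 × 0.12 × 0.88 × 0.8 = 456.2, with square root 21.36. With one-sided alpha 0.05 (z = 1.645):

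- HR 1.08: 0.07696 × 21.36 = 1.644; Φ(−0.001) = 0.500.
- HR 1.15: 0.13976 × 21.36 = 2.985; Φ(1.340) = 0.910.

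Both ends match. Two-sided 0.05 gives 0.376 and 0.847, and one-sided 0.01 gives 0.247 and 0.745; neither matches. A VATS share of 94/400 = 0.235 against everyone else gives 0.691 and 0.988, which does not match either. The calculation that was run is therefore robotic against all others, whatever the accompanying sentence calls it.

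**Step 2: group sizes.** Assume the 48/94/258 split holds for all 5400: robotic 0.12 × 5400 = 648, VATS 0.235 × 5400 = 1269, open 0.645 × 5400 = 3483.

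**Step 3: each planned robotic comparison, all else unchanged.**

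- Robotic versus VATS: n = 648 + 1269 = 1917; pA = 648/1917 = 0.338; n·pA·pB·pE = 343.2, square root 18.52.
- Robotic versus open: n = 648 + 3483 = 4131; pA = 648/4131 = 0.157; n·pA·pB·pE = 437.1, square root 20.91.

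| Comparison | HR 1.08 | HR 1.10 | HR 1.12 | HR 1.15 | HR for 80% power |
|---|---|---|---|---|---|
| Robotic vs all others (as sized) | 0.50 | 0.65 | 0.78 | 0.91 | 1.124 |
| Robotic vs VATS | 0.41 | 0.55 | 0.68 | 0.83 | 1.144 |
| Robotic vs open | 0.49 | 0.64 | 0.77 | 0.90 | 1.126 |

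Robotic versus VATS has 343.2/456.2 = 75% of the information in the sized comparison.

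**Step 4: sensitivity of robotic versus VATS.**

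- VATS share 15% to 40% (assumption, robotic share held at 12%): 0.37 to 0.46 at HR 1.08 and 0.77 to 0.87 at HR 1.15.
- Two-sided alpha 0.05: 0.30 to 0.74 across the hazard ratio range, against 0.38 to 0.85 for the pooled control.
- Event probability 0.6 (assumption): 0.34 to 0.73, against 0.41 to 0.83 pooled.

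The robotic-versus-VATS figure is below the pooled one in every case.

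**The case against.** The strongest reply is that little changes. Thoracotomy is the reference in the outcome models, and robotic versus thoracotomy loses only about one point. Section 3.3.4.2 names no direct robotic-versus-VATS survival test. The retrospective cohort is every eligible operation in 2016–2021, so recalculating power adds no patients. The plan already discloses power as low as 0.50, and it reports 95% confidence intervals that would show any imprecision. Uncertainty in the event probability matters as much: at 0.6 the pooled power itself falls to 0.41–0.83.

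Most of this stands, and it limits the point. It does not remove it, because robotic versus VATS is in the primary objective and has its own cost-effectiveness ratio, yet the only stated power belongs to a different contrast. The dependence on the event probability is a reason to state the conditions, not to leave the comparison unspecified.

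Applying the 48/94/258 split to all 5400 is an assumption, since it is given for the 400 prospective patients. It is a reasonable one: it comes from the same years as the retrospective cohort, and 48/400 equals the 0.12 used for survival. But section 3.3.1 warns that the codes for surgical approach have low sensitivity, so a range for the VATS share should accompany the result.

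Three stronger readings are tempting and are not supported:

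- A reader might infer that pooling could mask a survival difference between robotic surgery and VATS in the results. The plan estimates no pooled hazard ratio; pooling occurs only in the sizing.
- A reader might infer that the stated power is materially wrong for both comparators. For robotic versus open it is nearly right.
- A reader might infer that the robotic-versus-VATS power should be quoted when that cost-effectiveness ratio is interpreted. Once data exist, precision is read from the confidence interval, and section 3.4.4 varies the parameters over theirs.

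**Conclusion.** The point holds as a mismatch between the sizing and the planned comparisons. It is not an arithmetic error, because the stated range reproduces exactly. The shortfall that matters is confined to robotic versus VATS: 8 to 11 points across hazard ratios of 1.08 to 1.15, with the hazard ratio detectable at 80% power moving from about 1.12 to 1.14.

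The figures rest on an event probability of 0.8, an inferred one-sided alpha of 0.05, a null hazard ratio of 1, the 48/94/258 split applied to all 5400, and no variance inflation from inverse probability weighting. The existence of a gap does not depend on the exact alpha, event probability or VATS share within the ranges tried; its size does. The planned analyses themselves are unaffected.

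**What to change.** In section 3.3.4.1:

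1. Replace the single range with one power line per planned pairwise comparison. On the present inputs: robotic versus VATS, n = 1917, pA = 0.338, power 0.41–0.83; robotic versus thoracotomy, n = 4131, pA = 0.157, power 0.49–0.90. Section 3.4.1 also plans VATS versus open, so add that line: n = 1269 + 3483 = 4752, VATS share 0.267, power 0.68–0.98.
2. State the conditions beside the figures: event probability, alpha and sidedness, the approach shares with a range for VATS, and that no allowance is made for weighting.
3. Label 0.50–0.91 as robotic versus all other approaches combined, which is not a planned comparison, or delete it.
4. Correct the description of the varied hazard ratio as that of VATS, since the calculation uses the robotic share.

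The cost is a recalculation and a few lines of text. The only downside is a less favourable stated power for robotic versus VATS.
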